4.5. INDUCTION PHASE DOSING COMPLIANT POPULATION

The induction phase dosing compliant population includes any subject in the evaluable population who completes at least 85% of the dosing the induction phase. This population will be used for secondary analyses of efficacy endpoints.

4.6. STUDY DOSING COMPLIANT POPULATION

The study dosing compliant population includes any subject in the mITT population who completes at least 85% of the dosing for visits completed prior to discontinuation. This population will be used for secondary analyses of efficacy endpoints.

5. STATISTICAL METHODS

Descriptive statistical methods will be used to summarize the data from this study, with hypothesis testing performed for the primary and other selected efficacy endpoints. Unless stated otherwise, the term “descriptive statistics” refers to number of subjects (n), mean, median, standard deviation (SD), minimum, and maximum for continuous data and frequencies and percentages for categorical data.

All data collected during the study will be included in data listings. Unless otherwise noted, the data will be sorted first by subject number and then by phase (induction, maintenance), cycle/visit, and date.

Unless otherwise specified, all statistical testing will be two-sided, and will be performed using a significance (alpha) level of 0.05.

The statistical analyses will be conducted with the SAS® software package version 9.2 or higher. All analyses will be subject to formal verification procedures. Specifically, results will be verified utilizing independent programming prior to issuance of the draft statistical report. All documents will be verified by the lead statistician to ensure accuracy and consistency of analyses.

5.1. SUBJECT DISPOSITION, DEMOGRAPHIC, AND BASELINE CHARACTERISTICS

The number of subjects enrolled into the study, the number in each analysis population, major protocol violations, number of subjects who discontinue early, reasons for discontinuation, and duration of treatment will be summarized in tabular format. Demographic and background characteristics (including baseline medical history and cancer history) will be summarized descriptively.

5.2. EFFICACY ANALYSIS

5.2.1. Primary Efficacy Endpoint

The primary outcome measure is the complete response rate in subjects with refractory /relapsed CIS or CIS plus papillary disease (i.e., cohorts 1 and 2) following the initiation of Vicinium therapy.

Patients who discontinue or die before Month 3 will be included in the denominator of the primary analysis.

For the primary efficacy endpoint analysis, the following conventions will be utilized in determining treatment failure or complete response at a given visit.

1. Subjects that have centrally read pathology findings ('CIS', 'any-grade T1', 'high-grade Ta') or centrally read cytology results ('High Grade Urothelial Carcinoma') that indicate treatment failure for a given visit will be considered to have treatment failure.
2. Subjects who met a treatment failure criterion at a previous visit are treatment failures at all subsequent visits.
3. Subjects who have discontinued the study on or prior to the visit and have missing data that would be necessary to generate response are considered non-CRs.
4. Subjects who do not meet criterion 1-3 are complete responders.

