## **14.1 Criteria for Response (in Subjects with CIS)**

The primary endpoint for this study is the complete response rate in subjects enrolled in Cohort 1 (see [Section 10](#)). These subjects with CIS will be considered to have a complete response if at the time of any disease status evaluation (per protocol every 13 weeks or any unscheduled evaluation) there is no evidence of high-grade disease (CIS, high-grade Ta or high-grade T1 disease) or disease progression (e.g., to muscle invasive disease). Subjects whose initial diagnosis was CIS who are found to have low-grade papillary disease at the time of an evaluation must have the low-grade disease resected by TURBT. Low-grade disease is not considered a treatment failure in these subjects and they may remain on study treatment following TURBT.

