Subjects with CIS (Cohort 1 or Cohort 2) will be considered to have a complete response if at the time of any disease status evaluation (per protocol every 13 weeks or any unscheduled evaluation) there is no evidence of high-grade disease (CIS, high-grade Ta or any grade T1 disease) or disease progression (e.g., to muscle invasive disease). Subjects whose initial diagnosis was CIS who are found to have low-grade Ta disease at the time of an evaluation must have the low-grade disease resected by TURBT. Low-grade Ta disease is not considered a treatment failure in these subjects and they may remain on study treatment following TURBT.

Date of Complete Response or Treatment Failure

Given that the cystoscopy, biopsy, and cytology assessments may be conducted on different dates, the date of complete response or treatment failure will be defined as the earliest assessment date of these assessments.

Duration of Response

Duration of Response will be analyzed for subjects with CIS with or without papillary disease (Cohort 1 + Cohort 2) who achieve complete response using a Kaplan-Meier (KM) product-limit method. It is defined as the number of days from the date of first occurrence of complete response to the date of documented treatment failure or death, whichever occurs first. Subjects who do not experience treatment failure or death will be censored at their last assessment of response.

Event

For the purposes of defining Event-Free Survival, an event is defined as treatment failure or death on or prior to treatment discontinuation. Because disease assessments are not recorded after treatment discontinuation, a death after treatment discontinuation will not be counted as an event so as not to artificially inflate EFS. Presence of upper or lower urinary tract urothelial carcinoma and having a cystectomy are not treated as events for analysis but do trigger special data handling in the event-free survival analysis.

Event-Free Survival

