3.3.9. Combining Data Across Panels

When data are combined across panels to create composite endpoints, like complete response, information will be combined in the following manner:

1. Data will be merged by visit for each subject.
2. Unscheduled and early termination data will be windowed according to the visit windows below. Additionally, data from visits where pathology, cytology, and cystoscopy are unexpected (i.e., Maintenance Month 4) will be windowed using the table below.
3. Data within a given visit window will be collapsed to the worst-case result. For example, if a subject has two central pathology assessments for a given visit one with 'CIS' and the other with 'No Tumor', the analysis result for the collapsed visit will be considered as 'CIS'.
4. The date corresponding to the collapsed visit will be the earliest observed date for the visit.

Analysis Visit	Study Days
Screening	-8 < Study Day < 1
Week 1	1 <= Study Day <= 49
Post Induction Phase	49 < Study Day <= 137
Maintenance Month 3	137 < Study Day <= 227
Maintenance Month 6	227 < Study Day <= 318
Maintenance Month 9	318 < Study Day <= 409
Maintenance Month 12	409 < Study Day <= 500
Maintenance Month 15	500 < Study Day <= 591
Maintenance Month 18	591 < Study Day <= 682

Maintenance Month 21	682 < Study Day <= 773
Long-term Follow up Month 3	773 < Study Day <= 864
Long-term Follow up Month 6	864 < Study Day <= 955
Long-term Follow up Month 9	955 < Study Day <= 1046
Long-term Follow up Month 12	1046 < Study Day <= 1137
Long-term Follow up Month 15	1137 < Study Day <= 1228
Long-term Follow up Month 18	1228 < Study Day <= 1319
Long-term Follow up Month 21	1319 < Study Day <= 1410
Long-term Follow up Month 24	1410 < Study Day <= 1501

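### SAP 5.2.1 omits T2 or higher from the pathologies that score a treatment failure, so applied literally it can count a muscle-invasive finding as a complete response at the visit where it is found

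*SAP*

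**What the plan says.** SAP 5.2.1 gives four conventions for deciding treatment failure or complete response at each visit in the primary analysis:

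- Rule 1 scores as failures "Subjects that have centrally read pathology findings ('CIS', 'any-grade T1', 'high-grade Ta') or centrally read cytology results" of high-grade urothelial carcinoma, where these indicate failure.
- Rule 2: "Subjects who met a treatment failure criterion at a previous visit are treatment failures at all subsequent visits".
- Rule 3: subjects who have left the study by the visit and "have missing data that would be necessary to generate response are considered non-CRs".
- Rule 4: "Subjects who do not meet criterion 1-3 are complete responders".

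The definitions elsewhere are wider. SAP 3.3.7 allows a complete response only if "there is no evidence of high-grade disease (CIS, high-grade Ta or any grade T1 disease) or disease progression (e.g., to muscle invasive disease"). Protocol 14.1 has the same structure: "there is no evidence of high-grade disease (CIS, high-grade Ta or high-grade T1 disease) or disease progression (e.g., to muscle invasive disease"). The treatment-failure definitions in SAP 3.3.7 and Protocol 14.2 also count progression to muscle-invasive disease as failure. The PFS definition in SAP 3.3.7 gives T2 or more advanced disease as its example of progression.

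For several results in one window, SAP 3.3.9 says: "Data within a given visit window will be collapsed to the worst-case result". Its only example is CIS taking precedence over no tumour.

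**The concern.** Rule 1 is a short list of result values and rule 4 is a default to success. With that structure, any adverse pathology missing from the list is scored as a response. The missing value is the most advanced bladder finding the trial can record. On the same date, one biopsy could be a PFS event and a treatment failure under SAP 3.3.7, and a complete response on the primary endpoint under SAP 5.2.1.

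The planned sensitivity analyses would not reveal this. SAP 5.2.3 tests missing central reads after an abnormal cystoscopy, and low-grade Ta counted as failure; neither touches T2. The protocol cannot settle the matter either, because the SAP introduction says the SAP prevails where the two differ.

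**Working it through.** **Step 1. Apply rules 1 to 4 literally.** Take a subject with no earlier failure and with central pathology and cytology both present at the visit.

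| Central pathology | Cytology negative or suspicious | Cytology high-grade urothelial carcinoma |
|---|---|---|
| No tumour | CR | Failure |
| Low-grade Ta | CR (intended) | Failure |
| CIS, high-grade Ta or any-grade T1 | Failure | Failure |
| T2 or higher | **CR** | Failure |

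The T2 cell on the left is the error. Rule 1 does not list the value. Rule 2 needs an earlier failure. Rule 3 needs missing data, and a central T2 reading is not missing. Rule 4 then applies, even if the subject leaves the study at that visit.

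**Step 2. Follow the subject forward.** Protocol 10 withdraws subjects with treatment failure from the study, and SAP 3.3.7 (Event) says disease assessments are not recorded after treatment discontinuation. At the next visit the data are then missing after discontinuation, and rule 3 scores non-CR. The false response therefore sits mainly at the visit of detection.

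**Step 3. Reproduce the plan's own precision figures.** The inputs are from SAP 3.1: an assumed CR rate of 0.30, a two-sided exact 95% interval, and at least 77 evaluable subjects with early relapsed/refractory CIS. The Clopper-Pearson lower limit is the 0.025 quantile of Beta(x, n − x + 1). With x = 0.30n:

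- n = 121: 0.2201 (plan 0.220)
- n = 95: 0.2102 (plan 0.210)
- n = 76: 0.2002 (plan 0.200)

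The table reproduces.

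**Step 4. Size per subject.** One misclassified subject adds 1/n to the CR rate. At n = 77 this is 1/77 = 1.3 points. If all 57 further places went to Cohort 2, n would be 77 + 57 = 134 and the figure 1/134 = 0.7 points.

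**Step 5. Illustration at n = 77.** Suppose 24 subjects are scored CR and k of them have T2. The documents give no T2 rate. An assumed 1% to 5% of subjects gives 0.01 × 77 = 0.8 to 0.05 × 77 = 3.9, about 1 to 4. Those with high-grade cytology are caught by rule 1, so fewer would be affected.

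| k | True CRs | Rate | Exact 95% interval |
|---|---|---|---|
| 0 | 24 | 31.2% | 0.211 to 0.427 |
| 1 | 23 | 29.9% | 0.1997 to 0.414 |
| 2 | 22 | 28.6% | 0.189 to 0.400 |
| 3 | 21 | 27.3% | 0.177 to 0.386 |
| 4 | 20 | 26.0% | 0.166 to 0.372 |

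**The case against.** The best defence is that treatment failure is a defined term. SAP 3.3.7 includes centrally read progression in it, rule 1 speaks of findings that indicate treatment failure, and nothing in SAP 5.2.1 says it replaces the definition. SAP 3.3.7 also counts discontinuation for treatment failure or recurrence as failure, and Protocol 11.3 requires study drug to stop after treatment failure. A programmer working from SAP 3.3.7 would score T2 correctly. This shows what was intended. It does not repair the rule: the list carries no wording that makes it illustrative, rule 1 does not cite SAP 3.3.7, and the discontinuation provision is not repeated in SAP 5.2.1.

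The defence is stronger on consequences. A reader might infer four things that the documents do not support:

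- **That the subject stays a responder at later visits.** Rule 2 refers to any treatment-failure criterion, not only to rule 1, and can be read with SAP 3.3.7. After withdrawal, rule 3 catches most later visits in any case.
- **That duration of response is prolonged in subjects already in response.** Under SAP 3.3.7 it ends at documented treatment failure, which includes progression. Only a subject whose first CR is the T2 visit enters the set wrongly.
- **That the worst-case collapse turns a visit with both CIS and T2 into a CR.** SAP 3.3.9 gives T2 no rank, so this outcome is possible but not stated.
- **That one subject could decide whether the trial succeeds.** The 0.20 limit is a sizing target for a 12-month rate in early relapsed/refractory CIS. The SAP primary endpoint is the 3-month rate in Cohorts 1 and 2, and SAP 5.2.2 sets no 0.20 criterion. One responder at the boundary crosses 0.20 at other sample sizes too: the lower limit is 0.195 for 28/100 and 0.204 for 29/100.

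**Conclusion.** Wrong as written. The operative rule for the primary endpoint gives a result that contradicts the SAP's own definitions and the protocol: centrally read T2 or higher, without a listed pathology or high-grade cytology, is scored CR at the visit of detection. Since the SAP's primary time point is 3 months, that may be the visit that matters most.

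The bias has one direction: it can raise the CR rate but not lower it. It is 1.3 points per affected subject at n = 77, mainly at one visit, plus wrongful entry into the duration-of-response set when that visit is the first CR. The contradiction rests on the text alone. The total effect depends on the number of isolated T2 findings, which is unknown, so the 1 to 4 subjects above are illustrative and probably an upper range under the assumed rate. The crossing of 0.20 in the table shows sensitivity to a single subject; it is not a change in a stated trial conclusion.

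**What to change.** - **SAP 5.2.1, rule 1:** add centrally read T2 or more advanced disease to the pathology list. Alternatively, have rule 1 cite the full SAP 3.3.7 treatment-failure definition, keeping its separate handling of upper and lower tract disease.
- **SAP 3.3.9:** state that T2 or higher is the worst category in the collapse and counts as failure.
- **Duration of response:** use the same definition for entry to the set and for the end of response.

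Do not add progression on imaging to rule 1. SAP 3.3.7 asks for centrally read evidence of progression, describes radiographic reads as local, and says radiographic upper or lower tract malignancy is not treatment failure. An imaging criterion would create a new conflict.

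The cost is a line of text in each place and a line of derivation code. The sample size does not change. The reported CR rate stays the same or falls by the number of subjects reclassified.

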A treatment-emergent laboratory toxicity is defined as an increase of at least one toxicity grade from the baseline assessment at any post baseline assessment. For defining treatment-emergent laboratory events, it is assumed that a laboratory assessment obtained on Day 1 with missing collection times occurred prior to the initiation of study drug. If the relevant baseline assessments are missing, then any graded abnormality (i.e., at least Grade 1) is considered as treatment-emergent. For the grading of severity of the laboratory toxicity, the CTCAE v 4.03 will be used.

Concomitant Medications

Concomitant medications are those medications taken on or after the initiation of study drug.

Previous Medications

Previous medications are those medications taken and stopped prior to initiation of study drug.

Treatment Failure

Treatment failure is defined as an event or events that demonstrate the study drug, Vicinium, is not able to achieve or maintain a response in the subject's bladder cancer. Specifically, these events include:

- Subjects whose diagnosis at study entry was CIS or high-grade papillary disease will be considered to have a treatment failure if at the time of any disease status evaluation (per protocol every 13 weeks or any unscheduled evaluation) there is centrally read evidence of high-grade disease (CIS, high-grade Ta or any grade T1 disease) or disease progression (e.g., to muscle invasive disease).
- Low-grade Ta disease is not considered a treatment failure in these subjects and they may remain on study treatment following TURBT. Low-grade Ta disease at the time of evaluation must have the low-grade Ta disease resected.
- Subjects with positive centrally-assessed urine cytology without histologic, cytologic or locally read radiographic evidence of upper or lower urinary tract malignancy will be considered as no longer in complete response and hence, as having a treatment failure.
- Subjects with histologic, cytologic or radiographic evidence of upper or lower urinary tract malignancy will not be considered to have treatment failure but will have study therapy discontinued.
- Subjects who are discontinued due to treatment failure or for recurrence will be considered as treatment failure

Complete Response

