5.2.3. Sensitivity Assessments for the Primary Efficacy Analysis

Given that complete response is assumed in cases where there is no evidence of treatment failure, it is important to evaluate the impact, if any, of missing data on the primary efficacy analysis. To this end, a sensitivity analysis will be conducted where subjects who have a missing centrally read pathology and/or centrally read cytology at a visit where there was an abnormal cystoscopy will be imputed as a treatment failure for that visit if the subsequent visit indicates treatment failure. A second sensitivity analysis will be performed where subjects with low grade Ta are treated as a failure.

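### SAP 5.2.1 omits the SAP 3.3.7 criterion that discontinuation for treatment failure or recurrence is a failure, so a few such subjects can default to complete response

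*SAP*

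**What the plan says.** SAP 3.3.7, under Treatment Failure, lists several ways to fail. The last is discontinuation itself: "Subjects who are discontinued due to treatment failure or for recurrence will be considered as treatment failure".

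SAP 5.2.1 gives the conventions for classifying a visit in the primary analysis:

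- Rule 1 covers "Subjects that have centrally read pathology findings" of CIS, any-grade T1 or high-grade Ta, or a central cytology of high-grade urothelial carcinoma.
- Rule 2 carries failure forward: "Subjects who met a treatment failure criterion at a previous visit are treatment failures at all subsequent visits".
- Rule 3 makes non-responders of "Subjects who have discontinued the study on or prior to the visit and have missing data that would be necessary to generate response".
- Rule 4 is the default: "Subjects who do not meet criterion 1-3 are complete responders".

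The reason for discontinuation is not an input to any of the four. SAP 5.2.3 acknowledges that "complete response is assumed in cases where there is no evidence of treatment failure". Its first sensitivity analysis takes a visit with an abnormal cystoscopy and a missing central read, which "will be imputed as a treatment failure for that visit if the subsequent visit indicates treatment failure".

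**The concern.** The two sections define failure differently, and 5.2.1 is the one that produces the primary CR rate. Someone stopped because the disease failed or recurred is a failure under 3.3.7. Under 5.2.1 the same person can be a complete responder at the visit that led to stopping. SAP Section 2 places the primary CR rate at 3 months, which is the first visit where this can happen.

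The omission works in one direction. Removing a failure criterion can turn failures into responders but never the reverse. In a single-arm, open-label trial there is no comparator in which the effect could cancel.

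It also affects the duration of response. SAP 3.3.7 dates both response and failure to the earliest assessment of the evaluation. A subject coded CR under 5.2.1 and failed under 3.3.7 at the same visit could therefore enter that analysis with a response of zero length.

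**Working it through.** **Logic.** Take a subject stopped for failure or recurrence and apply both sections to the visit that led to stopping.

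| Central read at that visit | Left the study by the visit date | SAP 5.2.1 | SAP 3.3.7 |
|---|---|---|---|
| Qualifying | Either | Failure (rule 1) | Failure |
| Present, non-qualifying | No | CR (rule 4) | Failure |
| Present, non-qualifying | Yes | CR (rule 4), if nothing needed is missing | Failure |
| Missing | No | CR (rule 4) | Failure |
| Missing | Yes | Non-CR (rule 3) | Failure |

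The sections disagree in three of the four rows without a qualifying central read. Rule 2 acts only on later visits, so it does not change the visit in the table.

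**Timing in rule 3.** SAP 3.3.9 gives a collapsed visit the earliest date observed in its window. A decision to stop normally follows the assessments, so on that date the subject would usually not yet have left the study. If the visit instead means the whole post-induction window (after Day 49 to Day 137), rule 3 reaches more of the subjects whose read is missing. Section 5.2.1 does not say which is meant.

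**Sensitivity analysis.** The first analysis in 5.2.3 needs a failure at the next visit. SAP 3.3.7 says disease assessments are not recorded after treatment discontinuation, and Protocol 10.6 continues the 13-weekly evaluations only for subjects without treatment failure. The trigger will therefore often be absent. Discordant reads, where the central result is present but non-qualifying, are outside that analysis altogether.

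**The plan's own figure.** SAP 3.1 uses an exact two-sided 95% interval at P = 0.30. The lower limit is the 0.025 quantile of Beta(x, n − x + 1), with x = 0.3n:

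- n = 121: 0.2201; n = 95: 0.2102; n = 76: 0.2002; n = 77: 0.2008.

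These match the table (0.220, 0.210, 0.200). In whole subjects at n = 77:

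- 23/77 = 29.9%, lower limit 19.97%
- 24/77 = 31.2%, lower limit 21.1%

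**Effect per subject.** SAP 4.3 and 5.2.1 make Cohorts 1 and 2 together the primary population, whose size is not stated. SAP 1.1 plans at least 77 in Cohort 1 and up to 57 in Cohorts 2 and 3 combined. The assumed range is therefore 77 to 77 + 57 = 134, the upper end being reached only if Cohort 3 were empty.

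- N = 77: 1/77 = 1.3 points
- N = 134: 1/134 = 0.75 points

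**Illustration.** The number affected, k, is an assumption. The starting rate of about 30% is the planning value, which SAP 3.1 attaches to 12 months.

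| N | CRs under 5.2.1 | Lower limit | k recoded as failure | Rate | Lower limit |
|---|---|---|---|---|---|
| 77 | 23 | 19.97% | 1 | 28.6% | 18.8% |
| 77 | 23 | 19.97% | 3 | 26.0% | 16.6% |
| 100 | 30 | 21.2% | 2 | 28.0% | 19.5% |
| 134 | 40 | 22.3% | 3 | 27.6% | 20.2% |
| 134 | 40 | 22.3% | 5 | 26.1% | 18.9% |

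**The case against.** The strongest reply is that the protocol nearly closes the gap. Protocol Section 14 requires central review of all cytology and biopsy samples, Section 14.4 classifies both on the central reading, and note 3 to Table 7 ties discontinuation to a positive biopsy or a positive cytology. A subject stopped for failure under those rules will normally have met rule 1 already. This stands, and it is why the count should be small. What remains is stopping on local judgement and central reads that are missing or discordant.

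A second reply is that central reading may properly overrule the investigator: the first criterion in 3.3.7 itself asks for centrally read evidence. A reader might infer that every such CR is a wrong call about the disease. The documents do not support that. They show that the SAP contradicts itself, and the upward direction is measured against 3.3.7, not against the truth.

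Third, rule 2 could be read as importing the 3.3.7 criterion. That would settle later visits but leave the visit that led to stopping.

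A reader might also infer that rule 3 can never apply when central data exist, or that the subject is always still on study at Month 3. Neither is settled. An unsatisfactory cytology, or one central read without the other, could count as missing. Protocol Section 10 says treatment failures are withdrawn from the study, while Section 11.3 withdraws them from study drug and keeps subjects who stop treatment in follow-up. Those passages need to be reconciled.

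**Conclusion.** The inconsistency holds on the text. At the visit that led to stopping, 5.2.1 can return a complete response for a subject whom 3.3.7 calls a failure. The conditions are that the central read is missing or non-qualifying and that rule 3 is not met. Relative to 3.3.7, the CR rate can only be raised.

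The cost is 0.75 to 1.3 points per subject over the assumed range of 134 down to 77. The total cannot be computed, because no count of such subjects is given. A reader might infer a large inflation of the primary result. The documents do not support that, since stopping is based on central reads. A small count could still matter near the planning reference: at N = 77, the step from 23 to 24 responders is what takes the lower limit above 0.2. That value comes from the sample-size statement, and the current text sets no formal success rule on it.

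**What to change.** Add to SAP 5.2.1: *A subject taken off study drug because of treatment failure or recurrence, as described in 3.3.7, is a treatment failure at the visit whose assessment led to discontinuation and at all later visits, unless the only finding was low-grade Ta or upper or lower urinary tract disease.* The exceptions are needed because 3.3.7 does not count those findings as failure. Report the central-read-only classification as a sensitivity analysis. State also what leaving the study means in rule 3, and which visit date it is compared with.

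The cost is modest. Reasons for discontinuation are already recorded (Protocol 11.3) and summarised (SAP 5.1), but each discontinuation must be linked to an assessment visit, and the documents do not show that this link exists. The tract-disease exception may need source review, because the SAP revision history reports that the collected data could not determine such disease. The CR rate may come out slightly lower.

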3.3.4. Missing Data and Outliers

Every effort will be made to obtain required data at each scheduled evaluation from all subjects who have been enrolled.

See section 3.3.5 for details of imputing missing dates. Unless otherwise specified, all other missing data will not be imputed.

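### A subject still on study whose evaluation is missed or unevaluable is scored as a complete responder, and the one missing-data sensitivity analysis is too narrow to bound the effect

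*SAP*

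**What the plan says.** SAP 5.2.1 sets four rules for scoring a visit. Rule 1 makes a subject a failure on positive central pathology or high-grade central cytology. Rule 2 carries failure forward. Rule 3 covers "Subjects who have discontinued the study on or prior to the visit and have missing data" needed to derive response, and makes them non-CR. Rule 4 takes the rest: "Subjects who do not meet criterion 1-3 are complete responders". Early losses stay in the analysis: "Patients who discontinue or die before Month 3 will be included in the denominator of the primary analysis".

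SAP 5.2.3 acknowledges the assumption: "Given that complete response is assumed in cases where there is no evidence of treatment failure". Its remedy is one missing-data sensitivity analysis. In it, a subject with an abnormal cystoscopy and a missing central read "will be imputed as a treatment failure for that visit if the subsequent visit indicates treatment failure". The other sensitivity analysis concerns low-grade Ta, not missing data. SAP 3.3.4 adds no rule for response data: "Unless otherwise specified, all other missing data will not be imputed".

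SAP 3.3.7, defining an event for event-free survival, disregards deaths after treatment has stopped and gives this reason: "Because disease assessments are not recorded after treatment discontinuation".

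The protocol says what an evaluation must contain. Table 6 requires cystoscopy and a first cytology at each 13-week evaluation. It also requires directed biopsy of suspicious areas, biopsies across the bladder when cystoscopy is clear but the first cytology is suspicious or positive, and a second cytology when the first is suspicious. Protocol 14.4 includes unsatisfactory among the possible cytology results.

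**The concern.** Rule 4 does not ask for a single negative finding. It turns the absence of information into a success for any subject who has not previously failed and is not recorded as off study. The trial has one arm, so no control group is subject to the same default. The CR rate and its lower confidence limit are the central efficacy evidence, and the default moves both in one direction relative to a rule that counts unevaluable visits as non-response. If even a few subjects are affected, a reader of the final tables cannot separate documented responses from assumed ones, because no planned CR table counts all missing or unevaluable visits as non-CR.

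**Working it through.** **Step 1: apply the rules to each kind of visit** (no earlier failure, no positive central read).

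| Subject at the visit | Rule | Score | Re-scored under SAP 5.2.3? |
|---|---|---|---|
| Off study, data missing | 3 | non-CR | Not needed |
| On study, visit missed | 4 | CR | No, there is no cystoscopy |
| On study, clear cystoscopy, unsatisfactory cytology | 4 | CR | No, cystoscopy is not abnormal |
| On study, suspicious cystoscopy, no central biopsy read, failure at next visit | 4 | CR | Yes |
| Same, but next visit absent or not a failure | 4 | CR | No |
| Off treatment, in follow-up, not assessed | 3 or 4, depending on how discontinuation is recorded | non-CR or CR | No |

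The worst-case collapsing in SAP 3.3.9 does not help. It works on results present in a window and has nothing to act on when the window is empty.

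**Step 2: reproduce the plan's own figures.** SAP 3.1 uses a two-sided 95% Clopper-Pearson interval at an observed rate of 0.30. The lower limit is the 2.5% quantile of Beta(x, n − x + 1) with x = 0.30n. This gives 0.2201 at n = 121, 0.2102 at n = 95 and 0.2002 at n = 76, matching the table (0.220, 0.210, 0.200). At the planned n = 77 it is 0.2008.

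**Step 3: whole subjects at n = 77.**
- 23 CRs: 29.9%, interval 0.1997 to 0.4138.
- 24 CRs: 31.2%, interval 0.2109 to 0.4274.

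The lower limit therefore exceeds 0.20 from 24 CRs upward.

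**Step 4: size of the shift.** Let m be the share of CIS subjects on study but unevaluable at the visit, and p the true CR rate. The documents give no value for m, so 2%, 5% and 10% are assumptions. Missingness is taken as unrelated to response.
- Present rule: (1 − m)p + m
- Unevaluable counted as non-CR: (1 − m)p
- Gap between the two rules: m
- Inflation of the present rule over the truth from this source: m(1 − p)

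At p = 0.30 the present rule gives 31.4%, 33.5% and 37.0%. The alternative gives 29.4%, 28.5% and 27.0%.

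More generally the inflation is m × q, where q is the share of unevaluable subjects who are truly non-responders. It runs from 0 (q = 0) to m (q = 1). For example, 5 of 77 is 6.5%. At q = 0.7 that adds 6.5 × 0.7 ≈ 4.5 points. It adds the full 6.5 points only if all five are true non-responders.

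**Step 5: chance that the lower limit exceeds 0.20**, that is P(at least 24 of 77) from the binomial with the rates in step 4.

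| m | p = 0.20, present rule | p = 0.20, unevaluable = non-CR | p = 0.30, present rule | p = 0.30, unevaluable = non-CR |
|---|---|---|---|---|
| 0 | 1.4% | 1.4% | 45.4% | 45.4% |
| 2% | 3.2% | 1.1% | 56.0% | 40.8% |
| 5% | 9.3% | 0.7% | 70.7% | 34.2% |
| 10% | 30.6% | 0.4% | 88.2% | 24.0% |

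**The case against.** The rule is not a blanket default. Rule 3 makes study discontinuations with missing data non-CR, early losses stay in the denominator, and SAP 3.3.7 counts anyone discontinued for failure or recurrence as a failure. Rule 3 can also score a true responder who leaves as non-CR. All of this stands. It follows that the net bias against the true rate is not certain in sign. What is certain is that the rate is never below the one obtained by counting all unevaluable visits as non-CR.

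Four stronger readings are tempting, and the documents do not support them.

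- **Subjects who stop treatment become responders at every later visit.** A reader might infer this from rule 3, which speaks of leaving the study, set beside "Because disease assessments are not recorded after treatment discontinuation". But Protocol 10 says that subjects meeting drug-discontinuation criteria are withdrawn from the study, which would bring them under rule 3. Protocol 10.6, 11.3 and 14 call for continued disease evaluation after treatment stops, SAP 3.3.9 provides windows out to long-term follow-up Month 24, and the footnote to the EFS censoring table limits the unrecorded assessments to discontinuation for an adverse event. This is an ambiguity to settle, not demonstrated inflation.
- **Duration of response fills with false responders.** SAP 5.2.2 censors at the last non-missing response assessment, so later default responses do not lengthen it. SAP 3.3.7 dates response from an actual assessment, so a wholly unassessed subject has no start date. Only a partly assessed subject could enter wrongly.
- **Growing missingness at 6 to 24 months undermines the primary result.** SAP section 2 sets the primary endpoint at 3 months and the later rates as secondary. At 3 months the evaluation decides entry to Maintenance and the window is wide (after Day 49 to Day 137), so wholly unassessed subjects should be least common there.
- **Ignoring cystoscopy is itself an error.** Under the protocol a suspicious cystoscopy alone is not failure, because it leads to biopsy. Relying on central reads in an open-label trial is defensible. Likewise, no biopsy is needed when cystoscopy and cytology show no disease. The gap is only a required biopsy that was not done or not centrally read.

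**Conclusion.** The concern holds for subjects not recorded as off study. Rule 4 scores their missed or unevaluable evaluations as complete responses, and the analysis in SAP 5.2.3 cannot bound the effect because it leaves most such visits unchanged. The coverage of subjects who are off treatment but still followed is unclear and needs a definition.

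The size cannot be read from the documents. The figures above rest on assumed missing rates and on missingness unrelated to response. They use n = 77, which was planned for Cohort 1 with a 12-month rate, whereas the SAP primary is the 3-month rate in Cohorts 1 and 2 pooled. They are illustrations, not forecasts. The 20% level is the SAP's sizing target; the SAP states no success threshold for CR. Within those limits, one defaulted subject can move the lower limit across 20% at the planned size. At a true rate of 20%, 2% to 10% unevaluable raises the chance of excluding 20% from 1.4% to between 3.2% and 30.6%. This should be corrected, since a stated scoring rule gives a wrong result on its plain reading and the data needed to repair it are already collected.

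**What to change.** Keep rules 1 and 2. Replace rules 3 and 4 in SAP 5.2.1 with:

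> CR at a visit requires a documented evaluation: cystoscopy performed, an evaluable central cytology that is not positive, and every biopsy and second cytology required by Protocol Table 6 for those findings performed, with biopsies centrally read as negative for treatment failure and the second cytology evaluable and not positive. Any subject in the primary efficacy population who does not meet this at the visit is a non-CR, whether or not treatment or study has been discontinued.

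The reference to Table 6 matters. A shorter rule asking only for a clear cystoscopy and a cytology that is not positive would pass a suspicious cytology without the biopsies and second cytology the protocol requires. Footnote 3 to Protocol Tables 3 and 4 gives a different trigger for random biopsies (a positive cytology or two suspicious ones), so it must be reconciled with Table 6 before programming. The last clause of the replacement also removes the ambiguity about treatment versus study discontinuation.

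Report the number of missing or unevaluable subjects at each visit, and keep the present rule as a labelled sensitivity analysis.

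The cost is SAP wording and reprogramming from data already planned for listing (cystoscopy, central pathology, cytology). The CR rate may be somewhat lower, because some true responders with missing data will count as non-CR. In the illustration with a true rate of 30%, the chance that the lower limit exceeds 0.20 falls from 45.4% with nothing missing to 40.8%, 34.2% and 24.0% at 2%, 5% and 10% unevaluable. If few subjects are affected, the change costs almost nothing.
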